1.5 Dose Rationale and Risk/Benefits

Subjects will receive an IV infusion of 0.5 mg/Kg of ketamine hydrochloride over 40 minutes. The dose is based on antidepressant effects of patients with major depression reported in previous studies (Ibrahim et al., 2011; Zarate et al., 2006). The dose of ketamine will be determined by actual body weight.

The IV dose used for anesthesia ranges between 1 to 4.5 mg/kg (Elia & Tramer, 2005; Sinner & Graf, 2008). The median dose for analgesia is 0.4 mg/kg (Elia & Tramer, 2005), similar to that used for depression. The dose reported in the drug abuse literature is typically 1/8 g usually taken intranasally (see graphic below).

As a laboratory agent, ketamine has several desirable qualities. It has a short-half life; it is relatively easy to administer; it does not usually cause cardiovascular or respiratory depression and it has been well-studied in clinical settings (Reich & Silvay, 1989). Recent literature supports the safety of using ketamine as an ideal anesthetic for children emergency room settings because of its positive safety profile including lack of respiratory suppression (Dolansky et al., 2008). In the lower doses used for antidepressant treatment reported in the literature, short-term side effects are very infrequent, mild, and transient (Carpenter, 1999; Lahti et al., 2001). These side effects include perceptual and mood changes and impairment in memory, attention and abstract reasoning, euphoria, elevations in blood pressure, dizziness, and increased libido, as well as gastrointestinal distress, increased thirst, headache, metallic taste, and constipation (Reich & Silvay, 1989). In the long-term, subanesthetic doses yielded no reports of emotional or psychological problems, cognitive deficits, medical or neurological problems, cravings for ketamine, use outside the research setting, unusual perceptions, sluggishness, flashbacks or paranoid thoughts (Perry et al., 2007). These findings further document the lack of long-term effects previously reported with anesthetic doses of ketamine (Moretti et al., 1984) and support the FDA-approved drug insert about the safety of ketamine:

"Ketamine has a wide margin of safety; several instances of unintentional administration of overdoses of ketamine (up to ten times that usually required) have been followed by prolonged but complete recovery".

CONFIDENTIAL

2 Study Objectives

Primary Objective:

To determine the efficacy of repeated-dose subanesthetic IV ketamine among adolescent patients with treatment resistant depression (TRD). *Hypothesis:* Based on previous results in adults with TRD, we predict that response rates will improve over the course of six treatments of ketamine.

Secondary Objectives:

To explore the durability of antidepressant response to repeated dose of IV ketamine in a 6-week observational period. *Hypothesis:* Based on the inherent neuroplasticity in adolescence due to ongoing neurodevelopment, adolescents may show a more durable clinical response than has been seen in adults.

To study the neurobiological mechanisms of response to ketamine. We will explore how clinical improvement relates to change in brain function, brain connectivity, brain chemistry, and in peripheral blood biomarkers of neuroplasticity and cellular resilience.

3 Study Design

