3.2 Primary Study Endpoints

The primary outcome measure is response status as defined by Children's Depression Rating Scale (CDRS) (Poznanski, 1985) Responders will be defined as having a significant reduction in their CDRS score ($\geq 50\%$) whereas non-responders will be defined as subjects whose scores do not show such a significant reduction or whose score increase. The percent change will be calculated by the formula below (Tao, 2009):

$$(\text{Baseline CDRS} - \text{Exit CDRS}) / (\text{Baseline CDRS} - 17)$$

Baseline CDRS: CDRS score obtained on Visit 1 – Baseline Assessment (Section 6.1)
Exit CDRS: the latest CDRS score obtained on Visit 10 - Clinical Assessment (Section 6.6) or Visit 11-16 – Follow-up Period (Section 6.7)

CONFIDENTIAL

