3.3 Secondary Study Endpoints

1. Montgomery-Åsberg Depression Rating Scale (MADRS) (Montgomery & Asberg, 1979) score of $\geq 50\%$. The MADRS has been used in most previous ketamine studies in adults and is designed to be sensitive to change. Although it has not been validated in adolescents, it has been used in several previous treatment studies of adolescent depression (Berard et al., 2006; von Knorring et al., 2006).
2. The Clinician-Administered Dissociative States Scale (CADSS) (Bremner et al., 1998)
3. The Profile of Mood States-Adolescent Version (POMS-A) (Terry et al., 1999)
4. The Beck Depression Inventory-II (Beck, 1988) which has been validated for adolescents (Osman et al., 2004)
5. The four-item positive symptom subscale of the Brief Psychiatric Rating Scale (BPRS) (Overall, 1962) consisting of suspiciousness, hallucinations, unusual thought content, and conceptual disorganization.
6. Relapse will be defined as a CDRS score $\geq 50\%$ of the pre-ketamine baseline. The onset of relapse will be calculated as the day halfway between the date of relapse and the previous date of response.
7. Biological endpoints will include MRI-based measures and blood-based measures of neuroplasticity.
8. The Clinical Global Impressions Scale (CGI) (Guy, 1976)

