6.4 Visits 4-8 – 5 subsequent ketamine infusions

Participants will undergo a total of six ketamine infusions within a 2-week period (on a Monday-Wednesday-Friday schedule). The 5 subsequent treatments will be conducted in the same way the first treatment was conducted (please see section 6.3 for details), except the blood draw only occurs before the first and after the last infusion.

After the conclusion of the 6th ketamine infusion (after participants has past the “2 hour post infusion” time point during the 6th clinic visit). Participants will again have 20cc of blood drawn by venipuncture, which will be handled in the same way as other blood draws (see section 6.3 for further details).

If adolescent has experienced nausea or vomited during any prior infusion and PI has determined that pre-treatment with IV Ondansetron is appropriate for management of adolescent’s nausea symptoms, adolescent will receive IV Ondansetron at a dose of 0.15 mg /kg (up to 8 mg) via the same IV port established for infusion of ketamine immediately before the administration of ketamine.

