7.3 Statistical Methods

In the following analyses, primary outcome measures will include the “per protocol” population. The secondary measures will include the “intent to treat” population.

Primary analysis: Paired t tests will be conducted between the lowest score from the post-treatment assessments and the baseline symptom levels to assess the maximum effect of ketamine infusion on symptoms for each person.

Secondary Analyses:

1. We will calculate the time to relapse for each participant.
2. Biological Mechanisms:
 - a. Neuroimaging data: Paired t tests will be conducted to evaluate pre- and post ketamine treatment changes in measures of brain functional activation, connectivity, white matter microstructure and brain metabolite concentrations. These preliminary data will be used to identify responsive measures and estimate sample sizes that would be needed to use these measures as endpoints in future studies.
 - b. Bimolecular studies to examine mechanisms of cellular resilience (insulin challenge, cytokine testing, gene expression) will be conducted to evaluate change in these pathways before and after ketamine. Analyses will be conducted by [name] at Mayo Clinic. Peripheral blood mononuclear cells (PBMCs) will be isolated from whole blood and divided into two groups. The first group will not receive any treatment. RNA will be extracted and whole genome microarray will be performed using illumina's genome-wide gene expression arrays. Differential pre- versus post-ketamine mRNA levels will be quantified and bioinformatics pathway analysis will be used to identify key differences in molecular responses to ketamine. A second subset of PBMCs will be cultured and cryopreserved. Once all samples are collected cells will be immortalized to ensure sufficient tissue availability. The following two separate analyses will then be performed:

CONFIDENTIAL

- i. Group 1 PBMCs will be stimulated with insulin and intracellular Akt, mTOR, and GSK3 gene and protein levels will be quantified following 0, 5, 15, and 30 minutes of stimulation. This signaling pathway is implicated in mediating the antidepressant response to ketamine. Western blot and rtPCR techniques will be used to quantify protein and gene expression, respectively;

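### No planned analysis examines response across the six infusions, which is what the primary hypothesis predicts, although the MADRS series that could do so is already collected

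*Combined protocol and SAP*

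**What the plan says.** - **Hypothesis (Section 2).** The one hypothesis attached to the primary objective reads "we predict that response rates will improve over the course of six treatments of ketamine".
- **Primary endpoint (Section 3.2).** "The primary outcome measure is response status as defined by Children's Depression Rating Scale (CDRS"). It is formed once per person. The starting value is given as "Baseline CDRS: CDRS score obtained on Visit 1" and the exit value as "the latest CDRS score obtained on Visit 10" or at the follow-up Visits 11-16. All of those visits come after infusion 6.
- **Primary analysis (Section 7.3, repeated in the Study Summary).** "Paired t tests will be conducted between the lowest score from the post-treatment assessments and the baseline symptom levels".
- **Other analyses (Section 7.3).** The clinical one is "We will calculate the time to relapse for each participant"; the rest are imaging and blood measures. The interim look repeats the same list in the first ten subjects, with the aim of checking early support for the hypotheses.
- **Infusion-day scales (Sections 6.3 and 6.4).** Before and 2 hours after infusion 1 the staff-rated scales are the CGI, BPRS+, MADRS and CADSS. For infusions 2-6, "The 5 subsequent treatments will be conducted in the same way the first treatment was conducted". The CDRS is not listed.
- **MADRS (Section 3.3).** It is a secondary endpoint. The protocol notes "The MADRS has been used in most previous ketamine studies in adults and is designed to be sensitive to change", and also that it has not been validated in adolescents.

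**The concern.** The hypothesis describes a course: the share of responders rising as infusions accumulate. A test of each person's lowest score against baseline compares two values per person. It gives no response rate and carries no information about infusion number. A participant who responds after infusion 1 and one who responds only after infusion 6 can contribute the same difference.

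Followed exactly, the plan therefore ends without an answer to its own primary prediction. The interim analysis is meant to check support for the hypotheses, yet nothing on its list bears on this one. Section 5.2 makes preliminary evidence of efficacy a step towards a randomised placebo-controlled trial, so how response develops over the six infusions is worth estimating properly here.

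**Working it through.** **1. When is the CDRS taken?**

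| Time | CDRS? | Source |
|---|---|---|
| Visit 1 | yes | 6.1 |
| Day of infusion 1, before dosing | implied by the entry criterion (score of at least 36); not listed in 6.3 | 4.1 |
| After infusion 1, up to infusion 6 | none | 6.3, 6.4 |
| Visit 10 | yes | 6.6 |
| Visits 11-16 | yes | 6.7 |

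The number of scheduled CDRS scores between the first dose and the sixth is 0, so CDRS response by infusion number cannot be formed.

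**2. Does any analysis look across infusions?** Lowest score against baseline: no. Time to relapse: no. Imaging, gene expression and cell assays: no. Interim: the same list, so no.

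**3. Could the data answer the question?** Yes, on the MADRS. The scores before infusions 2, 3, 4, 5 and 6 and at Visit 10 give status after 1, 2, 3, 4, 5 and 6 infusions, with the score before infusion 1 as baseline. On the Monday-Wednesday-Friday schedule the first five fall 2 to 3 days after a dose. Visit 10 may fall anywhere within a week of the last one.

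**4. How precise would it be?** Section 7.1 gives no alpha, power, response rate or variance, so there is no figure of the plan's own to reproduce. Everything in this step rests on assumptions: n = 20, response rising linearly over six occasions from 25% to 60% or from 25% to 50%, and a latent normal variable with within-person correlation ρ.

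For the raw first-to-sixth change, P(both) = Φ₂(Φ⁻¹(p₁), Φ⁻¹(p₆); ρ), gain g = p₆ − P(both), loss l = p₁ − P(both), and SE = √{[g + l − (g − l)²]/n}.

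| Rise | ρ, first to sixth | g | l | SE |
|---|---|---|---|---|
| 25% to 60% | 0.4 | 0.402 | 0.052 | √(0.3317/20) = 12.9 points |
| 25% to 60% | 0.7 | 0.368 | 0.018 | √(0.2634/20) = 11.5 points |
| 25% to 50% | 0.4 | 0.324 | 0.074 | √(0.3346/20) = 12.9 points |
| 25% to 50% | 0.7 | 0.282 | 0.032 | √(0.2520/20) = 11.2 points |

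If correlation instead decays with lag from 0.4 or 0.7 at one step, the first-to-sixth value is 0.4⁵ = 0.010 or 0.7⁵ = 0.168, and the SE is about 14 to 15 points.

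Simulated power of a two-sided 5% t test on per-person slopes (20,000 trials per scenario; size about 4 to 5%):

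| Rise | n | Constant ρ 0.4 / 0.7 | Decaying, lag-1 0.4 / 0.7 |
|---|---|---|---|
| 25% to 60% | 20 | 85% / 94% | 65% / 66% |
| 25% to 50% | 20 | 58% / 71% | 40% / 40% |
| 25% to 60% | 15 | 72% / 83% | 53% / 53% |
| 25% to 50% | 15 | 45% / 55% | 31% / 31% |

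A rise that happens entirely between the first two occasions lowers power further: to 57-71% and 33-43% at n = 20 with constant correlation. The simulated test is not the GEE model suggested below, whose own size and power were not checked.

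**5. The looser reading.** Suppose the hypothesis means only response by the end of the course. The matching quantity is then the CDRS response proportion, and Section 7.3 gives no estimate, interval or reference rate for it. An exact 95% interval for 10 responders out of 20 would run from 27% to 73%.

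**The case against.** The strongest reply is that the stated objective is efficacy of repeated dosing, and the hypothesis may only mean that patients will have improved by the end of six infusions. That fits a single response status per person. It is a fair reading, but it leaves a gap: the endpoint is a response status, while the analysis is a test of mean change at each person's best point.

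A second reply is that Section 7.3 refers to t tests in the plural, names no scale and takes the lowest post-treatment score, so infusion-day MADRS values may enter that minimum. This stands. It would be too strong to say that the infusion-day data are ignored; the documents support only that no analysis examines their course.

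Third, this is an uncontrolled 20-person pilot. That argues for estimation over a formal test, and against presenting any power figure as a promise. It does not argue for leaving the prediction unexamined.

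Fourth, a slope over infusions is confounded with elapsed time, and the Visit 10 interval differs from the others, so waning could distort the last point. Both objections are correct and limit what the added analysis can show.

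**Conclusion.** The point holds. As a course across infusions, the primary hypothesis is not addressed by any planned analysis and cannot be addressed on the CDRS. On the looser reading, the CDRS response proportion is still not estimated.

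A reader might infer more than this, and the documents do not support it:

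- That the trial cannot examine its hypothesis at all. It can, on the MADRS, without new data.
- That no CDRS is ever taken on an infusion day. Section 4.1 requires one before the first dose. Being pre-dose, it does not change the conclusion, but Sections 4.1 and 6.3 need reconciling.
- That adding the analysis would give a well-powered test of accumulating benefit. With 20 participants, power on the assumed rates is about 65-94% (25% to 60%) or 40-71% (25% to 50%). It is lower with fewer completers or an early rise. In one arm the slope cannot separate dose number from time.

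The size figures depend on assumed rates and correlations that are not in the documents. The finding itself does not depend on them.

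**What to change.** Add to Section 7.3, for all participants with at least one infusion:

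1. MADRS response, defined as a reduction of at least 50% from the score before infusion 1, taken from the scores before infusions 2-6 and at Visit 10.
2. The response proportion with its 95% CI after each infusion, and the number contributing at each point.
3. A slope over infusion number with its 95% CI, from a GEE logistic model with a small-sample variance correction or a mixed model on the MADRS score.
4. A sensitivity analysis without Visit 10, because of its variable interval after the last dose.

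Also report the CDRS response proportion with an exact 95% CI, stating which visit supplies the exit score. In Section 3.3, word the MADRS endpoint as a reduction of at least 50%; at present it reads as a score. Reconcile Section 4.1 with Section 6.3 on the first-day CDRS. Mark the infusion-day ratings in the Section 6.8 table, which shows no interview or questionnaire on those days.

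**Cost.** Wording and one model, with no new visits or data. The CDRS stays the primary endpoint. Two drawbacks should be stated in the plan: by the protocol's own account the MADRS is not validated in adolescents, and the slope describes a time course, not a cumulative dose effect. If the sponsor prefers not to add the analysis, the alternative is to reword the Section 2 hypothesis to match what will be analysed.

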| PHA | Phytohemagglutinin |
| PHI | Protected Health Information |
| PI | Principal Investigator |
| POMS-A | Profile of Mood States – Adolescent |
| REPA | Report of External Professional Activities |

CONFIDENTIAL

| | |
|-------|--|
| SAE | Serious Adverse Event |
| SHAPS | Snaith-Hamilton Pleasure Scale |
| TRD | Treatment-Resistant Depression |
| TEPS | Temporal Experience of Pleasure Scale |
| UTox | Urine Toxicology Screen |
| VA | Veterans' Affairs |
| WASI | Weschler Abbreviated Scale of Intelligence |

Study Summary

| | |
|---------------------------------------|--|
| Title | Open-label intravenous subanesthetic ketamine for adolescents with treatment-resistant depression |
| Protocol Number | CTSI 22225 |
| Phase | 2 |
| Methodology | Single group open-label pilot study |
| Study Duration | 2 years |
| Study Center(s) | University of Minnesota |
| Objectives | To determine the efficacy of repeated-dose subanesthetic IV ketamine among adolescent patients with treatment resistant depression. |
| Number of Subjects | 20 |
| Diagnosis and Main Inclusion Criteria | Male and female adolescents aged 12 to 18 with the presence of recurrent major depressive disorder without psychotic features. |
| Study Product, Dose, Route, Regimen | IV infusions of 0.5mg/kg of Ketamine hydrochloride over a 40-minute infusion period. Participants will receive a total of 6 doses over a 2-week period. |
| Duration of administration | 2 weeks |
| Reference therapy | Not applicable. |
| Statistical Methodology | 
The maximum effect of the ketamine infusions on symptoms for each participant will be assessed by conducting paired t tests between the lowest score from the post-treatment assessments and the baseline symptoms levels.
 
The time to relapse for each participant will be calculated and an average relapse time for the group will be reported.
 
Exploratory analysis will be done on changes in brain function, connectivity and chemistry, as well as in peripheral blood biomarkers.
 |

1 Introduction

This document is a protocol for a human research study. This study will be conducted according to US and international standards of Good Clinical Practice (FDA Title 21 part 312 and International Conference on Harmonisation guidelines), applicable government regulations and Institutional research policies and procedures.

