1.4 Clinical Data to Date

Randomized, double-blind, saline-controlled trials in adults with TRD have demonstrated that a single, subanesthetic infusion of intravenous (IV) ketamine at 0.5 mg/kg over 40 minutes can produce a rapid (within 2 hours) antidepressant response (Ibrahim et al., 2011; Zarate et al., 2006). Recent evidence suggests that serial doses of ketamine may be even more effective and may lead to more prolonged remission (aan het Rot et al., 2010; Murrough et al., 2012). Our current research with using serial dosing of IV ketamine among adult veterans with TRD over a 2-week period has shown promising results, with a response rate of 92% among the 12 participants to date.

Our motivation to test the efficacy of IV ketamine in adolescents with TRD stems in part from our encouraging experience testing repeated-dose IV ketamine in adult veterans with TRD (PI [name]) at the Veterans' Affairs (VA) Medical Center in Minneapolis (Shiroma, *Journal of Affective Disorders* 2013, *in press*). Patients receive 6 infusions of IV ketamine 0.5mg.kg over 60 minutes, with infusion visits occurring 3 times weekly for 2 weeks with no "wash-out" period. So far, as indicated below, a 90% cumulative response rate has been observed. The duration of response (i.e. time to relapse) has been considerably longer than other studies (i.e. 2-3 weeks (Murrough et al., 2013)). At 4 weeks, 50% of the patients in our study have still not relapsed. Ten adults have completed treatment to date.

[figure not shown]
With its rapid onset of action, ketamine provides an ideal tool for the study of biomarkers in major depressive disorder (MDD). Prior studies have used neuroimaging, including functional magnetic resonance imaging (fMRI) (Scheidegger et al., 2012), positron emission tomography (PET) (Carlson et al., 2013), and magnetoencephalography (MEG) (Salvadore et al., 2009; Salvadore et al., 2010), and proton magnetic resonance spectroscopy (proton MRS) (Salvadore et al., 2012) in ketamine trials to further elucidate the underlying biological mechanisms of MDD. We have been developing tools for examining neural circuitry in adolescents with MDD (Cullen et al., 2009; Cullen et al., 2010) which we plan to apply in the proposed study to examine neural mechanisms of ketamine action.

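### The durability hypothesis compares adolescents with adults, but the only planned summary is an average relapse time with no rule for non-relapsers, no interval and no named adult value

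*Combined protocol and SAP*

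**What the plan says.** Section 2 sets a secondary objective, "To explore the durability of antidepressant response to repeated dose of IV ketamine in a 6-week observational period". Its hypothesis, based on adolescent neuroplasticity, is that "adolescents may show a more durable clinical response than has been seen in adults".

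Two sentences describe the analysis. The Study Summary says: "The time to relapse for each participant will be calculated and an average relapse time for the group will be reported". Section 7.3 says: "We will calculate the time to relapse for each participant". Section 3.3 defines relapse on the CDRS and dates it halfway between the relapse visit and the previous visit in response. Section 6.7 provides six weekly follow-up visits for everyone, whether or not they responded.

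The adult evidence is in Section 1.4. For the group's own six-infusion series in veterans, the duration of response "has been considerably longer than other studies (i.e. 2-3 weeks" in a cited adult study). It adds: "At 4 weeks, 50% of the patients in our study have still not relapsed", and "Ten adults have completed treatment to date".

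No section states which adult figure is the reference, how a participant without a relapse enters the average, or what interval goes with it.

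**The concern.** A relapse time is known only for participants who relapse while being observed. Follow-up stops at week 6, so participants with the longest responses have no relapse time, and an average needs some convention for them. Leaving them out biases the average short, because it discards the most durable responses. Setting them to 6 weeks also understates the true mean, but by less. The plan does not choose.

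The adult reference is also open, and the two figures in Section 1.4 are of different kinds. One is a duration in weeks, not identified as a mean or a median. The other is a proportion at a fixed time. An adolescent average cannot be compared directly with that proportion.

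With both choices open until the data are seen, the same results could be reported as supporting or not supporting longer durability in adolescents. Section 2 links that durability to neurodevelopment, so a difference due to counting convention, regimen or site could be read as an effect of age. Section 5.2 presents this pilot as the step before a randomized trial, so a misleading durability figure could carry into its planning.

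**Working it through.** **The plan's own figure.** There is none to reproduce for durability: no error rate, margin or benchmark is given, and Section 7.1 bases the sample of 20 on adult studies without a calculation.

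**Inputs from the protocol.** N = 20 (Section 3.1). Adult response rate: "a 90% cumulative response rate has been observed" (Section 1.4). Weekly visits to week 6 (Section 6.7). Halfway dating of relapse (Section 3.3). Half of the group's adults not relapsed at 4 weeks (Section 1.4), read as a median of about 4 weeks.

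**Assumptions.** 20 × 0.90 = 18 responders; exponential relapse times; clock starting at the last infusion; no dropout. Adolescents are given the same 4-week median as the group's own adults, so they have no true advantage over them.

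**Step 1: who does not relapse.** The relapse-free proportion at t weeks is 2^(−t/4). At 6 weeks it is 2^(−1.5) = 0.354, so about 35% have no observed relapse. The true mean is 4/ln 2 = 5.8 weeks.

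**Step 2: the average under each convention.** With q = 2^(−1/4) = 0.841, the chance of relapse in week k is q^(k−1)(1 − q): 0.159, 0.134, 0.113, 0.095, 0.080 and 0.067 for weeks 1 to 6. Each relapse is dated k − 0.5, and Σ(k − 0.5) × probability = 1.619.
- Non-relapsers left out: 1.619 / (1 − 0.354) = 2.5 weeks.
- Non-relapsers set to 6 weeks: 1.619 + 6 × 0.354 = 3.7 weeks.

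Neither is close to 5.8.

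**Step 3: how often the average exceeds an adult figure** (simulation, 18 responders, no true advantage over the group's own adults).

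| Adult value | Non-relapsers at 6 weeks | Non-relapsers left out |
|---|---|---|
| 2 weeks | over 99% | 83% |
| 2.5 weeks | 99% | 46% |
| 3 weeks | 92% | 15% |
| 4 weeks | 30% | 0.2% |

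Reading across the 3-week row, the convention alone moves the answer from 92% to 15%. Reading down the first column, the choice of adult value moves it from over 99% to 30%.

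**Step 4: sensitivity.** With 10 responders, the chances of exceeding 3 weeks are 85% and 21%. With Weibull shapes from 0.7 to 1.5 and 18 responders, they are 87-97% and 4-51%. If the true median is instead 2.5 weeks, the average with non-relapsers at 6 weeks still exceeds 2.5 weeks in 81% of trials with 18 responders, because it is a mean compared with a median.

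**Step 5: precision of the adult figure.** If the 50% is 5 of 10, the exact 95% interval is 19% to 81%. The denominator is an assumption: Section 1.4 says ten completed treatment, not that ten were followed to 4 weeks, and half of nine responders is not a whole number.

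**The case against.** The strongest objection is that the plan contains no decision rule to criticise. The objective is to explore, the hypothesis says adolescents may do better, the average is only to be reported, and a randomized trial is named as the later step. This stands. It limits the point to the choice of summary and to how the comparison is described.

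A reader might infer something stronger: that the plan would usually declare adolescents more durable when they are no better than adults. The documents do not support that. It requires the 2-3 week figure as the reference, adolescents who truly match the group's own adults, non-relapsers counted at 6 weeks (or a median used instead of the stated average), and a bare comparison without an interval. Against the 4-week figure a favourable reading is the minority result: 30% for the average with non-relapsers at 6 weeks, and 41% for an observed 4-week relapse-free share above 50%. With relapsers only, the average exceeds 3 weeks in 15%.

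A reader might also infer that Section 1.4 contradicts itself. It does not. It attributes the two figures to different studies and says openly that its own is longer. With about ten adults they may not differ beyond chance: under a true median of 3 weeks, 5 or more of 10 would be relapse-free at 4 weeks with probability 36%.

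The objection does not remove the need to handle non-relapsers. Even a purely descriptive average cannot be interpreted without that convention.

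**Conclusion.** The point holds as a fault in the planned summary. An average relapse time does not answer a durability question when follow-up ends at 6 weeks and about a third of responders may not have relapsed. Under the assumptions above, the reported figure would be about 2.5 or 3.7 weeks, against a true mean of 5.8. It would exceed 3 weeks in 15% or 92% of trials, depending on a convention the plan does not state. The unnamed adult value widens the ambiguity.

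The exact percentages depend on 18 responders, exponential relapse and a 4-week median; the gap between conventions remains with 10 responders and with the other Weibull shapes tried. For an exploratory objective in a pilot, this is a correction worth making before analysis. It does not show that the plan is built to reach a favourable conclusion.

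**What to change.** In the Study Summary and Section 7.3, replace the average relapse time with a Kaplan-Meier analysis among responders, censoring participants without relapse at their last assessment. Report the relapse-free proportion at 4 and 6 weeks, and the median if reached, each with a 95% confidence interval. State when the clock starts, and fix the visit at which a participant counts as a responder for this analysis, because Section 3.2 allows the exit score to come from any visit from 10 to 16. Reconcile the 4-week observational period in Section 3.1 with the 6 weeks given there and in Sections 2 and 6.7.

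Show both adult figures from Section 1.4 beside the result, with the in-house interval (about 5/10, 19% to 81%, denominator assumed). Note that the relapse definition behind the adult figures is not given and that the in-house series is described with a different infusion duration. State that the comparison is historical and descriptive, and that this single-arm study will not conclude greater durability than in adults or attribute a difference to neurodevelopment.

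Do not add a rule that claims superiority when the adolescent lower limit exceeds 50%. It would treat about ten adults as known truth. With 18 responders it needs at least 14 relapse-free, and if the true proportion were 70% in both groups it would claim superiority in 33% of trials.

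The cost is a few sentences and no new visits or data. The downside is that the durability statement becomes less favourable and stays imprecise: 9 of 18 relapse-free at 4 weeks, for example, has an exact 95% interval of 26% to 74%.
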